## E3 Study Outcome Measurements and Ascertainment

Study outcomes will be measured in clinic either on iPads (PROMIS) which is linked to our REDCap system, or entered into REDCap by the research coordinator or occupational therapists.

# F Statistical Plan

## *F1* Sample Size Determination and Power

Various methods are identified in the literature for formulating a pilot study sample size. Julious recommends a minimum sample size of 12 per group as a rule of thumb and justifies this based on rationale about feasibility and precision about the mean and variance. So as to align our study with these recommendations, we plan to enroll 50 patients total in our pilot/feasibility study.

Approximately 100 patients per year undergo surgical intervention (either IB or LRTI) for CMC OA at Washington University. Assuming a 50% randomization rate for this study, a sample size of 100 produces a two-sided 95% confidence interval with a lower limit of 0.404 and upper limit of 0.596 when the sample proportion is 0.5. The primary goal of the trial is to assess feasibility and to obtain estimates for planning a larger, more definitive study to detect meaningful changes in clinical outcome measures.

## F2 Analysis Plan and Statistical Methods

Patient demographic and clinical characteristics will be summarized using means (standard deviation, SD) or median (25th, 75th) for continuous variables and frequency (percentage) for categorical variables. The recruitment rate (95% confidence interval) will be reported as the number randomized out of the total number of participants approached to participate in the study (screened). Reasons for not wanting to participate will be summarized and reported. The effect sizes and variability of the PROMs for each group will be reported and used to determine the sample size for a larger definitive trial. Differences in PROMs between LRTI and IB at 6 weeks and 3 months will be examined using a two-sample t-test and differences in categorical outcomes (return to work/activity, yes/no, at 3 months) using Pearson chi-squared test. Changes over time will be evaluated graphically to see the trajectory of change over follow-up and for assessing critical time points to inform future study design parameters. Objective parameters will be summarized for each group using descriptive statistics. The significance level will be 0.05 for all tests due to the exploratory nature of the study.

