Hand surgeons, however, continue to perform LRTI secondary to the desire to provide mechanical support for the thumb metacarpal and to avoid the exposed Kirschner wires (K-wires) associated with simple trapeziectomy. Recently, techniques have been described that provide immediate internal suspension of the thumb metacarpal after trapeziectomy without requiring prolonged immobilization or painful K-wires. Internal brace (IB, **Figure 2)**, a technology used in ligament augmentation in lateral ankle instability, syndesmosis injuries, and scapholunate ligament reconstruction , has been used at our institution for thumb CMC OA with encouraging outcomes in the short-term (unpublished data). The IB procedure allows the patient to forego postoperative casting or K-wire pinning and return to all activities at 6 weeks.

**Figure 2**: Illustration of internal brace procedure. Trapeziectomy is performed in standard fashion. Longitudinal traction is applied to the thumb. A suture anchor with suture tape is inserted into a drill hole at the radial aspect of the thumb metacarpal base. A second suture anchor is inserted into a drill hole at the radial base of the index metacarpal such that the suture tape suspends the thumb at the natural groove. Thumb position and tension are then assessed.

To date, the literature lacks high level clinical evidence to define IB's role in the treatment of thumb CMC OA. A prospective, randomized controlled trial (RCT) is required to compare the procedure's effectiveness in relieving pain and restoring function against that of LRTI. Therefore, we propose a pilot RCT comparing patient-reported outcomes following IB and LRTI to establish feasibility and generate effect size and variability estimates for a definitive, subsequent RCT (Aims 1 & 2). Recognizing that objective clinical measures such as thumb range of motion, grip/pinch strength, radiographic outcomes, and complications/need for additional surgery are critical in measuring IB's effectiveness against LRTI, we will characterize the two procedures with respect to these parameters along with return to work/activity (Aim 3).

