## C Study Objectives

#### C1 Study Aims and Rationale for Selection of Outcome Measures

Aim 1: Establish feasibility of a definitive trial by determining the proportion of eligible subjects who agree to randomized treatment and determining the followup retention rate. Rationale: To date, no studies have compared IB and LRTI for thumb CMC OA. Our study will assess the feasibility of a prospective RCT comparing outcomes of the two procedures. Hypothesis: A prospective RCT comparing outcomes of IB and LRTI is feasible, as defined by the ability to successfully recruit and randomize  $\geq$ 50 patients over the course of 1 year with a follow-up retention rate of  $\geq$ 90%.

Aim 2: Estimate effect sizes and variability in patient-reported outcomes for planning a definitive, two-arm RCT. Rationale: We will assess patient-reported outcomes (PROMIS UE/physical function, VAS pain, VAS satisfaction) following IB and LRTI. Effect size and variability estimates are required to inform the design of a future definitive trial. Hypothesis: IB will produce superior patient-reported outcomes to those of LRTI at 6 weeks and 3 months.

Aim 3: Characterize objective clinical outcomes (thumb range of motion, grip/pinch strength, radiographic outcomes, and complications/need for additional surgery) and to identify differences in return to work/activity following IB and LRTI at three months. Rationale: Objective clinical outcomes are important predictors of patient function after surgery for thumb CMC OA. IB offers an expedited return to work and activity by allowing patients to forego postoperative casting. Hypothesis: IB will produce similar objective outcomes to LRTI with a quicker return to work/activity.

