#### Feasibility

This study will assess the feasibility of recruiting patients into a prospective RCT and will obtain estimates to inform the sample size and design of a future adequately powered clinical trial. Specifically, we will be assessing randomization rate as calculated by dividing the number of patients randomized by the number of eligible participants and we will record the patient follow-up rate. In addition to our prospective study, we are

currently performing a retrospective cohort study comparing patient-reported outcomes of patients who have undergone LRTI and IB over the past 2 years. We anticipate that this retrospective study will also be instrumental in informing the design and sample size of a definitive RCT.

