#### E2 Schedule of Measurements, Visits, Safety and Adverse Events

Patients will undergo the surgery to which they are randomized, either LRTI or IB, performed by one of the seven Washington University orthopaedic hand surgeons. All patients will follow-up in clinic 2 weeks, 4 weeks, 3 months, and 1 year post-operatively.

PROMIS Physical Function and Upper Extremity scores will be collected at all clinic visits on iPad as per standard protocol for all patients presenting to a Washington University Orthopaedic Surgery clinic. Thumb ROM at carpometacarpal, metacarpophalangeal, and interphalangeal joints will be collected by a member of our team at 4 weeks, 3 months, and 1 year after surgery. Visual Analog Scale Pain and Satisfaction scores will be collected by a member of our team at 2 weeks, 4 weeks, 3 months, and 1 year after surgery. Visual Analog Scale Pain and Satisfaction scores will be collected by a member of our team at 2 weeks, 4 weeks, 3 months, and 1 year post-op. Grip and pinch strength (3-point and lateral vs contralateral values and vs preoperative values) will be collected at pre-op visit and all post-op visits except the 2 week visit. Radiographic subsidence will be measured via C-arm radiographs at 3 months and 1 year post-op. Complications (mild, moderate, severe) will be recorded throughout the course of the study at all time points. Mild complications will be defined as those with minor clinical impact (i.e., scar tenderness or sensory disturbances). Moderate complications will be defined as clinically relevant with delay in patient recovery, but not severe enough to necessitate revision surgery and resolve by

12 months after surgery (i.e., mild CRPS type I, tendinitis, neuromas treated with steroid injections). Severe complications will be defined as those which result in revision surgery, pain at rest, or impaired hand function at 12 month exam (i.e., severe CRPS type I or tendinitis and neuromas that do not improve with corticosteroid injections and require surgery). We will document patient return to work/activity at each follow-up appointment.

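### F2 names no important difference and sets no limit on using pilot PROM effects to size the definitive trial; its t-test leaves out pre-operative PROMIS, and its 6-week comparison has no listed visit

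*Combined protocol and SAP*

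**What the plan says.** On sizing the next trial, F2 states that the "effect sizes and variability of the PROMs for each group will be reported and used to determine the sample size" of that trial. Three other sections bear on this:

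- B1: "we propose a pilot RCT comparing patient-reported outcomes following IB and LRTI to establish feasibility and generate effect size and variability estimates".
- Aim 2 in C1: "Estimate effect sizes and variability in patient-reported outcomes for planning a definitive, two-arm RCT".
- F1, on the goal beyond feasibility: "to obtain estimates for planning a larger, more definitive study to detect meaningful changes in clinical outcome measures". No value is attached.

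The Feasibility part of D1 adds a second source, a retrospective cohort of the two procedures: "We anticipate that this retrospective study will also be instrumental in informing the design and sample size of a definitive RCT".

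No visible section gives an important difference, an SD or a power for any PROM. None says how the pilot and the cohort would be combined, or which PROM and time point would size the trial. F2 attaches a 95% CI to the recruitment rate but not to the PROM effects.

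On the comparison itself, F2 says: "Differences in PROMs between LRTI and IB at 6 weeks and 3 months will be examined using a two-sample t-test". On collection, E2 says: "PROMIS Physical Function and Upper Extremity scores will be collected at all clinic visits on iPad". On visits, E2 says: "All patients will follow-up in clinic 2 weeks, 4 weeks, 3 months, and 1 year post-operatively".

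**The concern.** Aim 2 exists to supply planning inputs, and F2 lists the effect size, not only the variability, among the inputs that will determine a sample size. A between-arm effect from a small pilot is a poor target. Pilots that overstate the effect lead to trials that are too small, and pilots that understate it lead to trials nobody can run. F2 contains nothing to prevent that use. Because it ties the effect sizes to each group, it also leaves open whether the between-arm effect is meant at all. A within-group effect cannot by itself size a two-arm comparison, so either reading leaves a gap.

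Two further matters affect the same estimates. The t-test makes no use of a pre-operative PROMIS score that appears to be collected. And one of the two planned comparison times, 6 weeks, matches no listed visit, so half of the planned PROM contrasts may have no data behind them.

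**Working it through.** **Inputs.** From the documents: 50 patients (F1); two arms in blocks of 4, 6 and 8 (2.d); retention of at least 90% (Aim 1); significance level 0.05 (F2). Assumed: 1:1 allocation, so 25 per arm (0.9 × 25 = 22.5, taken as 22, after attrition); two-sided tests; 80% power for the definitive trial; true standardised effects d of 0.3, 0.5 and 0.8.

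**The plan's own figure.** The only computed statistical figure is F1's interval for a 50% randomization rate with n = 100. The Wilson half-width is 1.96 × √(0.25/100 + 1.96²/(4 × 100²)) / (1 + 1.96²/100) = 0.096, giving 0.404 to 0.596. It reproduces, but it says nothing about the PROM effects.

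**Step 1: precision of the pilot effect.** SE(d) = √(2/n + d²/(4n)). For d = 0.5 and n = 25 this is √(0.08 + 0.0025) = 0.287, so the 95% CI is 0.5 ± 1.96 × 0.287 = −0.06 to 1.06. With 22 per arm the SE is 0.306 and the CI −0.10 to 1.10.

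**Step 2: sizing from the observed effect.** Per-arm n = 2 × ((1.960 + 0.842)/d)². A true d of 0.5 needs 63, 0.3 needs 175 and 0.8 needs 25.

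A trial sized from an observed d has under 50% power when that d exceeds (2.802/1.960) × the true d. For a true 0.5 the threshold is 0.715. The chance of exceeding it is about 1 − Φ((0.715 − 0.5)/0.287) = 1 − Φ(0.75) = 0.23 of all pilots. Among the 94% of pilots with an observed d above 0.05, that is about 0.24.

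Simulating 2,000,000 pilots per scenario at 25 per arm, and treating an observed d at or below a cutoff of 0.05 / 0.1 / 0.2 as not sizeable, gives:

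| True d | Correct n per arm | Not sizeable | 5th to 95th percentile of n per arm | Sized trials under 50% power |
|---|---|---|---|---|
| 0.3 | 175 | 19% / 24% / 36% | 24–1,934 / 23–883 / 22–313 | 40% / 43% / 51% |
| 0.5 | 63 | 6% / 8% / 14% | 16–774 / 16–518 / 15–254 | 24% / 25% / 26% |
| 0.8 | 25 | 0.4% / 0.7% / 1.7% | 9–134 / 9–129 / 9–113 | about 14% at each cutoff |

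With 22 per arm and true d = 0.5, the last column is 26% / 27% / 29%.

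**Step 3: precision of the pilot SD.** With 48 degrees of freedom the ratio of limit to estimate is √(48/χ²). The 95% limits are √0.695 = 0.83 and √1.561 = 1.25. The upper one-sided 80% limit is √1.211 = 1.10.

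**Step 4: fixed difference plus that upper limit.** The 5th / 50th / 95th percentiles of per-arm n are 146 / 209 / 287 for a 0.3 SD target, 53 / 76 / 104 for 0.5 SD and 21 / 30 / 41 for 0.8 SD: about a twofold spread in each case. The price is 1.10² = 1.21, for example 63 becoming 76.

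**Step 5: where the fixed difference does worse.** At 76 per arm and a true effect of 0.3 SD, power is Φ(0.3 × √(76/2) − 1.960) = Φ(−0.11) = 46%; at a true 0.4 SD it is 69%. With a 0.5 SD target and a true 0.3 SD, 73% of trials sized this way have under 50% power, against 40–51% for the pilot-effect rule. With a 0.8 SD target and a true 0.5 SD, it is 55% against 24–26%.

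**Step 6: adjusting for the pre-operative score.** The t-test's 95% half-width is t(48 df) × √(2/25) = 0.57 SD. With ANCOVA it is t(47 df) × √(2(1 − r²)/25) = 0.54, 0.49 and 0.41 SD at assumed correlations r of 0.3, 0.5 and 0.7.

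**Step 7: the 6-week comparison.**

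- A1, A2, Aim 2 in C1, and F2 all set PROM results at 6 weeks and 3 months.
- A1, D1 and E2 list visits at 2 and 4 weeks, 3 months and 1 year. A1 contains both statements.
- PROMIS is tied to clinic visits, and E2 lists the VAS times explicitly without 6 weeks.
- E3 places outcome measurement in clinic. D1 offers remote PROMIS only if patients miss follow-up.

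The 3-month comparison has a visit. The 6-week one has none listed.

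**The case against.** A reader might infer from F2 that the observed between-arm difference will be the target of the definitive trial. The text does not say so. B1 and the two-arm wording of Aim 2 favour that reading without settling it, while F1's reference to meaningful changes and the retrospective cohort point to other inputs. What is established is the absence of a rule, not a wrong rule. A later protocol can also set its own target, and no pilot data are lost meanwhile. All this stands and makes the first point conditional.

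The upper tail in the table is soft: at a true d of 0.5 its 95th percentile falls from 774 to 254 on the choice of cutoff alone. F1 puts the site's volume at about 100 operations a year, so a size of several hundred per arm would be noticed, not silently adopted. The firmer risk is the lower tail, which barely moves with the cutoff at true effects of 0.5 or 0.8.

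The fixed difference is not better in every case. Step 5 shows it doing worse when the true effect is below the chosen difference. That is the accepted meaning of powering for a stated difference, but it must be said. Nor does new wording alone settle the matter while no value, PROM or time point is named.

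References 26 to 30 are PROMIS sources that no visible passage cites, so a PROMIS rationale may be missing from the text available. Reference 30 concerns an important difference in distal radius fractures, and its use for thumb arthritis would need its own justification.

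The two-sample t-test is valid, so ANCOVA is a matter of precision only, and the gain is small at r = 0.3. On the visits, the postoperative regimen that D1 introduces is not visible and might mention a 6-week contact. One may not conclude that 6-week data will certainly be absent, only that no listed visit supplies them.

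**Conclusion.** The point holds in conditional form. F2 makes PROM effect sizes an input to the definitive sample size, and no visible text names an important difference or limits that use. If the between-arm estimate became the target, about a quarter of the trials sized from it would have under 50% power at an assumed true d of 0.5, about 14% at 0.8 and 40–51% at 0.3. These figures rest on the assumed allocation, power and true effects, since the documents give none. The pilot SD is precise enough to use.

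The 6-week mismatch needs no assumed numbers and is the firmest error in the documents, subject only to the regimen that cannot be seen. The ANCOVA point is a smaller suggestion.

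It would be wrong to infer that the pilot is invalid or that 50 patients are too few. Feasibility is the primary outcome, the PROM tests are declared exploratory, and neither the feasibility conclusion nor the pilot's size depends on any of this.

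**What to change.** 1. **Sizing rule.** In F2, commit to reporting the between-arm difference with its 95% CI and the pooled SD for each PROM and time point. Before anyone looks at outcome data by arm, name the PROM and time point that will size the definitive trial and an important difference for it, justified for thumb CMC osteoarthritis. Size from that difference and a conservative pilot SD, for example the upper one-sided 80% limit (about 1.10 times the estimate; other limits are defensible). Use the pilot effect and the retrospective cohort only to check that the difference is plausible. Cost: wording now, about 20% more patients in the definitive trial, and lower power, possibly lower than under the pilot-effect rule, if the true effect is below the chosen difference.

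2. **Baseline adjustment.** Analyse each PROMIS score by ANCOVA on arm and its own pre-operative score, and list that score by name in E2. Collection at all clinic visits implies that it exists. Report the residual SD and the baseline-to-follow-up correlation, and size from the residual SD only if the definitive trial will also use ANCOVA. Cost: one schedule line and a change of model.

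3. **Six weeks.** Reconcile A1, A2, Aim 2 and F2 with the visits in A1, D1 and E2, so that each PROM comparison time matches a scheduled collection. Which side changes is for the investigators to decide. The cost is wording if the comparison time moves, or an added collection if the schedule does.

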## A Introduction

## A1 Study Abstract

Carpometacarpal osteoarthritis (CMC OA) is a prevalent and disabling disease. Trapeziectomy with ligament reconstruction and tendon interposition (LRTI), the most frequently performed procedure for CMC OA, requires prolonged postoperative immobilization which limits patients' abilities to perform ADLs and to work. Trapezium excision and internal brace (IB) stabilization is a largely unstudied novel alternative to LRTI which allows an expedited return to work/activity. In this feasibility and pilot grant application, our overall objective is to investigate critical guestions to inform the planning of a definitive randomized controlled trial (RCT) comparing IB and LRTI for patients with CMC OA. Our central hypothesis is that a prospective RCT comparing LRTI and IB is feasible, and that IB will produce superior patient-reported outcomes to LRTI at 6 weeks and 3 months with an expedited return to work/activity. Our specific aims are to (1) establish feasibility of a definitive trial by determining the randomization rate and followup retention rate, (2) estimate effect sizes and variability in outcomes for planning a definitive RCT, and (3) characterize objective clinical outcomes (thumb range of motion, grip/pinch strength, radiographic outcomes, complications/need for additional surgery) and to identify differences in return to work/activity following IB and LRTI. To achieve our aims, we will randomize 50 patients as they present to the clinics of the 7 Washington University Orthopaedic Hand surgeons to LRTI (control) or IB (experimental). Patients will follow-up at 2 weeks, 4 weeks, 3 months, and 1 year post-operatively. Our primary outcome will be feasibility (randomization rate, follow-up retention rate). Secondary outcomes will be PROMIS and Visual Analog Scale Pain and Satisfaction scores at 6 weeks and 3 months, objective clinical outcomes (thumb range of motion, grip/pinch strength, radiographic outcomes, complications/need for additional surgery), and return to work/activity.

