## A2 Primary Hypothesis

Our central hypothesis is that a prospective, randomized trial comparing LRTI and IB is feasible, and that IB will produce superior patient-reported outcomes to LRTI at 6 weeks and 3 months with an expedited return to work/activity.

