Upon successful completion of the proposed research, we expect to (1) demonstrate that randomization into a prospective RCT comparing IB and LRTI is feasible, (2) obtain estimates to inform the sample size and design of a future adequately powered prospective RCT, and (3) show that IB produces superior patient-reported outcomes at 6 weeks and 3 months to LRTI while offering an expedited return to work/activity.

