## D Study Design

#### D1 Overview or Design Summary

Our study has been registered on ClinicalTrials.gov. All facets of our study design, analysis, and interpretation will adhere to Consolidated Standards of Reporting Trials (CONSORT) guidelines. Data will be managed using REDCap (Research Electronic Data Capture) electronic data capture tools hosted at our institution. REDCap is a secure, web-based application designed to support data capture for research studies, providing: 1) an intuitive interface for validated data entry; 2) audit trails for tracking data manipulation and export procedures; 3) automated export procedures for seamless data downloads to common statistical packages; and 4) procedures for importing data from external sources.

The research team will identify potential participants as they present to the clinics of one of our seven Orthopaedic Hand and Upper Extremity surgeons. The study population will consist of patients aged 50 years and older who are English-speaking and community-dwelling. These patients will have a confirmed diagnosis of isolated thumb CMC arthritis. Patients will not have carpal tunnel syndrome (to avoid outcome data confusion), rheumatoid/inflammatory arthritis, or a history of chronic opioid use. The research team will block randomize the participants into a control group (LRTI) and a comparison group (IB); block sizes will be 4, 6, and 8.

#### Study Aim 1

The team will review patients' medical records and radiographs to determine potential participants' eligibility. The team will recruit eligible individuals during their clinic appointments using an information form outlining the benefits and relative limitations of each procedure. Patients who are interested in participating in the study will undergo initial testing at their clinic appointment, at which time they can also provide informed consent. Feasibility will be recorded by means of randomization rate and follow-up retention rate throughout the enrollment process. In the event that a patient declines randomization into our study, we will record the patient's reason for declining.

Following the consent process, the study will proceed as follows:

- 1. Patient will undergo the surgery to which they are randomized, either LRTI or IB, performed by one of the seven Washington University orthopaedic hand surgeons.
- 2. All patients will follow-up in clinic 2 weeks, 4 weeks, 3 months, and 1 year postoperatively.

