Patients will undergo a standardized postoperative recovery and therapy regimen:

#### Study Aims 2 & 3

PROMIS Physical Function and Upper Extremity scores will be collected at all clinic visits on iPad as per standard protocol for all patients presenting to a Washington Orthopaedic Surgery clinic. Thumb Universitv ROM at carpometacarpal. metacarpophalangeal, and interphalangeal joints will be collected by a member of our team at 4 weeks, 3 months, and 1 year after surgery. Visual Analog Scale Pain and Satisfaction scores will be collected by a member of our team at 2 weeks, 4 weeks, 3 months, and 1 year post-op. Grip and pinch strength (3-point and lateral vs contralateral values and vs preoperative values) will be collected at pre-op visit and all post-op visits except the 2 week visit. Radiographic subsidence will be measured via C-arm radiographs at 3 months and 1 year post-op. Complications (mild, moderate, severe) will be recorded throughout the course of the study at all time points. Mild complications will be defined as those with minor clinical impact (i.e., scar tenderness or sensory disturbances). Moderate complications will be defined as clinically relevant with delay in patient recovery, but not severe enough to necessitate revision surgery and resolve by 12 months after surgery (i.e., mild CRPS type I, tendinitis, neuromas treated with steroid injections). Severe complications will be defined as those which result in revision surgery, pain at rest, or impaired hand function at 12 month exam (i.e., severe CRPS) type I or tendinitis and neuromas that do not improve with corticosteroid injections and require surgery). We will document patient return to work/activity at each follow-up appointment.

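### The patient-reported outcome comparison is planned at 6 weeks and 3 months, but the schedule collects no patient-reported outcomes at 6 weeks

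*Combined protocol and SAP*

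**What the plan says.** **Where the comparison is placed.** The analysis plan (F2) reads: "Differences in PROMs between LRTI and IB at 6 weeks and 3 months will be examined using a two-sample t-test". The central hypothesis (A2) is that "IB will produce superior patient-reported outcomes to LRTI at 6 weeks and 3 months with an expedited return to work/activity". The abstract (A1) lists as secondary outcomes "PROMIS and Visual Analog Scale Pain and Satisfaction scores at 6 weeks and 3 months". The expected results at the end of B1 are to "show that IB produces superior patient-reported outcomes at 6 weeks and 3 months to LRTI", and the Aim 2 hypothesis (C1) is that "IB will produce superior patient-reported outcomes to those of LRTI at 6 weeks and 3 months".

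**Where data are collected.** The same abstract says: "Patients will follow-up at 2 weeks, 4 weeks, 3 months, and 1 year post-operatively". D1 repeats this: "All patients will follow-up in clinic 2 weeks, 4 weeks, 3 months, and 1 year postoperatively". E2 gives the same four visits. On the instruments, D1 says: "PROMIS Physical Function and Upper Extremity scores will be collected at all clinic visits on iPad". D1 and E2 list VAS pain and satisfaction at the same four times as the visits. E3 says that outcomes are measured in clinic.

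The only provision for remote collection is under Potential Pitfalls in D1. It is a fallback for patients who miss follow-up.

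**The concern.** The hypothesis and its test sit at one set of times and the assessment schedule at another. They overlap only at 3 months. Both versions recur through the document, and the abstract contains both, so a reader cannot tell whether 6 weeks or 4 weeks is the slip.

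If the schedule is followed, the early half of the patient-reported comparison has no planned data. An analyst would then have to leave out a prespecified comparison or present 4-week data as if they were 6-week data. The two times may not be interchangeable. B1 describes rigid immobilization of 4 to 6 weeks as typical after LRTI, and says IB patients return to all activities at 6 weeks. A between-group contrast at 4 weeks may therefore estimate something different from one at 6 weeks.

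The 6-week effect size and standard deviation would also be missing when the definitive trial is planned. F1 counts planning estimates as part of the trial's primary goal.

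**Working it through.** The plan gives no calculated figure on this point. The only computed figure in its statistical section, the 95% interval of 0.404 to 0.596 for a randomization rate of 0.5 with n = 100 (F1), reproduces as a Wilson interval (0.4038 to 0.5962). It has no bearing here. The check is a comparison of time points.

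**Step 1. Count the statements that place the patient-reported comparison at 6 weeks.** A1 has two (hypothesis and secondary outcomes). A2, B1, C1 and F2 have one each. Total: 2 + 1 + 1 + 1 + 1 = 6.

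**Step 2. Count the schedule statements that use 4 weeks.**

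| Item | Where | Count |
|---|---|---|
| Visit list | A1, D1, E2 | 3 |
| VAS list | D1 (1), E2 (2, one a repeated sentence) | 3 |
| Thumb range-of-motion list | D1, E2 | 2 |
| Total | | 8 |

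Statements that schedule any collection at 6 weeks: 0. These counts show that neither version is an isolated typo. They do not show which is right, since much of the text is duplicated between sections.

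**Step 3. Match analysis times to collection times.**

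- Analysis times (F2): {6 weeks, 3 months}.
- Collection times (D1, E2): {2 weeks, 4 weeks, 3 months, 1 year}.
- Common to both: {3 months}. Without scheduled data: {6 weeks}, which is 1 of 2.

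**Step 4. Size in comparisons.** C1 names PROMIS upper extremity/physical function, VAS pain and VAS satisfaction. Reading this as four scales (an assumption, because F2 does not list them), 4 scales × 2 times = 8 comparisons, of which 4 × 1 = 4 fall at 6 weeks.

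**Step 5. Distance to the nearest visits.** Three months is 3 × (365.25 / 12) / 7 = 13.04 weeks. The gap between scheduled collections is 13.04 − 4 = 9.04 weeks. Six weeks is 6 − 4 = 2 weeks after one visit and 13.04 − 6 = 7.04 weeks before the next.

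**Step 6. Look for another route to 6-week data.**

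- No visit window maps the 4-week visit to 6 weeks.
- The remote option in D1 replaces missed assessments and adds no new time.
- Unscheduled clinic visits might produce a few PROMIS scores near 6 weeks, but these would be unplanned and self-selected.
- The other mentions of 6 weeks, in B1, concern recovery and not data collection.

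**The case against.** The strongest reply concerns weight. The primary outcome is feasibility, the comparison is secondary, and F2 calls the study exploratory. F1's sentence on planning estimates and F2's sentence on effect sizes and variability name no time point. As scheduled, group means and standard deviations would exist at all four visits, and F2 plans to plot trajectories. Planning for the definitive trial therefore largely survives. This stands, and it limits the damage to one early time point. It does not remove the problem, because 6 weeks is named in the central hypothesis and in the prespecified test.

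A second reply concerns missing text. D1 announces a standardized postoperative regimen whose content is absent from the text available for review, and that gap cannot be held against the plan. The regimen might include a 6-week clinic contact, and PROMIS would then be collected at it. This stands for the two PROMIS scales, whose absence at 6 weeks is established only for the available text. It does not help VAS pain and satisfaction, which have fixed collection times that exclude 6 weeks.

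A third reply is that the immobilization period in B1 describes usual practice and not this trial's regimen. That is correct, so any remark based on it must be conditional.

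**Conclusion.** The concern holds. In the available text, one of the two time points of the F2 comparison has no scheduled patient-reported data: 1 of 2 times, or 4 of 8 comparisons on the four-scale reading. The finding is firm for VAS. For PROMIS it assumes that the unseen postoperative regimen adds no 6-week clinic visit.

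The feasibility outcome and the 3-month comparison are unaffected. The point still needs correction, because the central hypothesis cannot be tested in full as planned and the missing scores cannot be obtained afterwards. The documents do not settle which time was intended.

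**What to change.** Before data collection, the sponsor should state the intended early time point and reconcile A1, A2, B1, C1 and F2 with D1, E2 and E3. There are two routes.

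**(a) Schedule a 6-week collection.** If the 4-week entry is the slip, correct the assessment schedule; VAS, range of motion and grip/pinch tied to that visit move with it. If the 4-week visit is intended, add one remote PROMIS and VAS questionnaire at 6 weeks. That would go beyond the present D1 fallback and needs changes to E2 and E3.

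**(b) Restate the hypothesis and the F2 test at a time that is collected.** If 4 weeks is chosen, label it so. Note that it may fall within the immobilization period B1 describes as typical after LRTI, so the contrast would include that difference in postoperative care. Six weeks is the end of the same range, so the same note belongs there if it applies under the trial's own regimen.

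Under either route, 4-week data should not be reported as 6-week results.

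**Cost.** Route (b), or correcting a slip under (a), needs wording changes and no added visit. The consent document, not available here, should be checked for visit times. The remote questionnaire adds one form per patient (50 × 1 = 50 in total) and mixes in-clinic with remote collection, which should be stated in the report.

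The documents do not show whether collection has begun. If it has, patients already past 6 weeks without a score cannot supply one, which favours (b).
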